## Summary

### 1. Test subject

efficacy and safety of B. subtilis spore

### 2. Test objective

The efficacy and safety of B. subtilis spore were evaluated with simulated oral tablet as control

### 3. Test vaccine

Test group: Oral approach, 1 capsule of B. subtilis spore once a day. No other medication.

Start in the morning on an empty stomach.

### 4. Overall design of test

This study was conducted in a single arm design.

### 5. Test population

Normal healthy people without disease. Excluded those with basic diseases such as hypertension, diabetes and hyperglycaemia. Test schedule

2021.4.01 – 2021.9.30

---

## Main body

### 1. Introduction

COVID-19 caused by severe acute respiratory syndrome corona virus 2 (SARS-CoV-2). By December 2020, it had infected more than 80 million people and killed more than 1.7 million people all over the world. Due to the lack of effective treatment, the development and use of COVID-19 vaccine had become an important strategy to control the novel pneumonia epidemic.

Covid-19 was a single strand plus RNA virus, whose exposed spike protein (S protein) and receptor binding domain (RBD) on S protein were the main targets for the design of Covid-19 vaccines. In March 2020, the Covid-19 vaccine developed by China based on adenovirus vector and the mRNA technology platform developed by the United States which were the first vaccines entering clinical trials, followed were DNA vaccine and inactivated vaccine. By the end of December 2020, there were inactivated vaccine, nucleic acid vaccine (DNA vaccine and mRNA vaccine), carrier vaccine, protein subunit vaccine, live attenuated vaccine, virus-like particles vaccine. The sixty vaccine candidates in six different technical routes were approved to enter clinical trials. Some vaccines had been approved for conditional marketing or emergency use.

Due to the different development technology routes of different COVID-19 vaccines, there were still different shortcomings in terms of safety, effectiveness, stability of transportation and storage, and capacity.

Although the safety of COVID-19 vaccines in phase III clinical trials had been reported to be good, there were still theoretical safety concerns. For example, live attenuated vaccines needed to replicate in the body and carry a risk of virulent atavism infection or transmission. DNA vaccines carried the risk of foreign DNA entering the body and integrating into the host genome, resulting in oncogene activation, or inactivation of tumor suppressor genes, or chromosomal instability. The synthetic materials and coating materials used in the synthesis of mRNA vaccines may be toxic and might cause apoptosis of the surrounding host cells.

In the introduction of the target product of the Covid-19, WHO proposed that the protection efficacy of the Covid-19 should be at least 50%. Among the four vaccines whose effectiveness had been announced, the inactivated vaccine had a protective efficacy of 79.34%, the carrier vaccine 62-90%, and the mRNA vaccine above 90%, all of which met the requirements. But in the context of COVID - 19 pandemic disease, unfavorable evaluation or directly compare the clinical efficacy of vaccine were appeared. That was because different vaccine clinical trial design and research field, the research results were different. Vaccine real protection effect still need to be extensively studied through subsequent large-scale phase IV

---

---

clinical trials or epidemiological studies after vaccinating.

In terms of storage and transportation of the Covid-19, mRNA vaccine required high storage conditions due to its unstable and easily degradable. A mRNA vaccine developed by the United States and Germany needed to be stored at -70°C. After thawing, vaccine vials could only be stored for 5 days in cold storage (2-8°C). The other mRNA vaccine was stable for only 30 days at 2-8 ° C and needed to be stored at -20 ° C.

Due to the need for virus culture process, the production of inactivated and attenuated vaccines required high bio-safety level and long production cycle, so there was some difficulty in scaling up production capacity.

This product was bacillus subtilis spore vaccine. Various types of vaccines such as mRNA, adenovirus and inactivated virus via injection route were developed to prevent the infection of SARS-CoV-2. Although some of them have already been approved to against the COVID-19 pandemics, various drawbacks including severe side effects and instability in storage may hinder their applications. *Bacillus subtilis* (*B. subtilis*) is a generally recognized as safe (GRAS) and endotoxin-free gram-positive bacterium, which has been extensively employed as a host for expression of recombinant proteins. Its dormant spores are extraordinarily resistance to harsh environment conditions in gastrointestinal tract. This feature makes it an ideal candidate for oral administration to resist the environment. In this study, an engineered *B. subtilis* spore expressing the spike protein receptor binding domain (sRBD) of the SARS-CoV-2 on the surface was developed, and the result proved that it successfully increased the neutralizing antibody against sRBD in unvaccinated mice and human individuals after oral administration. These findings may enable the use of *B. subtilis* spore as oral vaccine against COVID-19 in the future.

The oral vaccine presents antigen through the gastrointestinal mucosa and could produce an immune response similar to that of conventional injection through different immune pathways. With the development of medicine and molecular biology technology, great progress had been made in the study of oral vaccine in the presentation of mucosal antigen, which could effectively induce immune response and immune tolerance in the body. The toxicity of the vaccine was very low, and the LD50 could not be measured by oral or peritoneal route. According to the toxicity grading standard, it was basically non-toxic. Long-term toxicity, specific toxicity and reproductive toxicity studies did not show any biological damage. Experimental data showed that the vaccine was extremely safe and well tolerated by patients.

---

---

## 2. Test subject

efficacy and safety of Bacillus subtilis spore.

## 3. Test objective

The efficacy and safety of " Bacillus subtilis spore " were evaluated with simulated tablet as control

## 4. Overall design and arrangement of the test

### 4.1. Test design

This study adopted a one-arm experimental design. The whole study mainly collected qualified normal healthy people without disease from the hospital, and excluded people with basic diseases such as hypertension, diabetes, hyperlipidemia and so on. Once confirmed, they were assigned to administer 1 dose of Bacillus subtilis spore. Follow-up observation and efficacy examination were performed on days 7, 14, 21 and 28.

If subjects had significant laboratory abnormalities or side effect at the end of the study, they should be followed up to normal.

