### 4.2. Dose, method and course of treatment

Group	Dosage	Usage	Survey
Test group	1 Bacillus subtilis spore capsule at a time	Oral administration, once	28 days

Vaccine time window: Oral administration of the vaccine would be given immediately after the subjects were selected.

Essential medicines: over-the-counter medicines such as vitamins and minerals were allowed.

---

Medicines prohibited: antibiotics, thrombolytic drugs, anticoagulants, insulin,  $\beta$ -blockers, adenosine preparations, leucocyte adhesion inhibitors, other antioxidants, free radical scavengers, etc.

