### **6.2. Vaccine packaging**

---

Single 1 capsule, individually packed.

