### **6.3. Administration**

Test group: Oral approach, 1 capsule B. subtilis spore once a day. No other medication.

Start in the morning on an empty stomach.

Control group: Oral approach, 1 simulated tablet once a day. No other medication.

Start in the morning on an empty stomach.

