## 10.2. Statistical analysis method

### 10.2.1. Statistical analysis of population

Intent-to-treat, ITT: The ITT population was defined as all patients who were randomized to double-blind treatment and had received at least one trial vaccine treatment with a corresponding efficacy evaluation.

Per-Protocol, PP: PP population referred to the patients who had completed the vaccine treatment according to the protocol, and had completed all the evaluation contents without any significant deviation from the protocol.

Safety Population: All patients who had used the study vaccine once and had undergone at least one safety assessment were randomized to be included in the study's safety population. Safety population was the main population for safety evaluation in this study.

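### The regimen is contradictory: sections 4.1 and 4.2 give one capsule once, while the Summary and 6.3 give one capsule daily with no stated number of days

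*Combined protocol and SAP*

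**What the plan says.** All places are in the combined protocol and SAP.

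**Text that sets a single dose**

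- Section 4.1 (Test design): "they were assigned to administer 1 dose of Bacillus subtilis spore".
- Section 4.2 (Dose, method and course of treatment): the usage column of the table reads "Oral administration, once". The time window below it adds that "Oral administration of the vaccine would be given immediately after the subjects were selected".

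**Text that sets daily dosing**

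- Summary, section 3 (Test vaccine): "1 capsule of B. subtilis spore once a day".
- Section 6.3 (Administration; numbered 6.4 in the contents list): "Test group: Oral approach, 1 capsule B. subtilis spore once a day", followed by "Control group: Oral approach, 1 simulated tablet once a day".

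**Text that bears on the regimen without fixing it**

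- Section 6.2 (Vaccine packaging): "Single 1 capsule, individually packed".
- Section 10.2.1 defines the safety population as "All patients who had used the study vaccine once", with at least one safety assessment.
- Section 10.1 makes completion of the treatment plan a condition of the per-protocol set, and 10.2.1 has a similar condition.

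The 28 days in the 4.2 table stand in the survey column and match the follow-up visits on days 7, 14, 21 and 28. They are an observation period, not a course length.

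**The concern.** Once and once a day are different interventions, and both stand in the protocol as instructions. Someone looking up how to give the product would naturally turn to 6.3, which has the daily wording and no stopping point.

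Three things depend on the answer.

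- **Meaning of the primary readings.** The main efficacy indicator is immunogenicity (7.1), examined on days 7 to 28. The number of capsules taken and the time since the last one determine what those measurements represent. The same holds for the safety findings.
- **Exposure of healthy volunteers.** The Introduction describes a spore engineered to carry a SARS-CoV-2 antigen. A daily instruction without an end date puts no ceiling on the amount taken.
- **Membership of the per-protocol set.** Under 4.2, a subject who took one capsule on day 0 has finished treatment. Under 6.3, nobody can be classified, because there is no course length to complete.

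The vaccine distribution form (6.4) and the subject diary card (11.1) might allow actual intake to be reconstructed. However, the text says only that they record distribution and vaccination status; it does not mention capsule counts.

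**Working it through.** The plan has no figure of its own to reproduce here, so the check has two parts: a comparison of the dosing statements, then the arithmetic of what the daily wording would permit.

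**Comparison of the text**

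| Place | Amount | Frequency | Number of days |
|---|---|---|---|
| 4.1 | 1 dose | single | not needed |
| 4.2 | 1 capsule | once, right after selection | not needed |
| Summary 3 | 1 capsule | daily | not given |
| 6.3, test group | 1 capsule | daily | not given |
| 6.3, control group | 1 simulated tablet | daily | not given |

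The rest of the document does not settle the matter.

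- *Towards a single dose:* the immediate-administration window in 4.2 and the safety-population wording in 10.2.1.
- *Towards repeated dosing:* withdrawal for discontinuing the product (5.3), sets that require at least one treatment (10.1, and the ITT definition in 10.2.1), and causality factors based on stopping and re-using the vaccine (8.3).
- *Neutral:* individual packing of capsules (6.2), which suits either regimen.

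Section 6.3 also doses a control group, although 4.1 describes a one-arm design. That suggests 6.3 was carried over without correction. This favours 4.1 and 4.2, but it does not withdraw the instruction in 6.3, and the Summary repeats the daily schedule for the test group.

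**Exposure implied by daily dosing**

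Suppose dosing runs daily from day 0 for n days, so the last capsule falls on day n − 1.

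- Capsules taken = n.
- Days from last capsule to the day 28 visit = 28 − (n − 1) = 29 − n.

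| n | Capsules | Days from last capsule to day 28 |
|---|---|---|
| 1 (4.1 and 4.2) | 1 | 29 − 1 = 28 |
| 3 | 3 | 29 − 3 = 26 |
| 7 | 7 | 29 − 7 = 22 |
| 14 | 14 | 29 − 14 = 15 |
| 28 | 28 | 29 − 28 = 1 |

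If day 28 itself were also a dosing day, the figures would be 29 capsules and 0 days. Only the first row comes from the documents. Every n above 1 is an assumption made to show the range, and the last row applies only if daily dosing fills the whole survey period, which no section states.

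**The case against.** The strongest reply is that the intended regimen is clear enough. Section 4.2 is the section on dose and course of treatment. It has the only regimen table, that table is complete, and 4.1 agrees with it. The daily text has no end date and so is not a complete rival regimen; it looks like template residue. Repeated dosing would require staff to disregard 4.1 and 4.2, and nothing in the documents shows that anyone was dosed more than once. On this view the matter is a wording correction.

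Part of this stands. A single dose is the better reading, and there is no evidence of mixed dosing. But calling 6.3 a leftover explains the error without removing it. The daily instruction appears in two places, one of them the section a dosing team would consult. Text elsewhere that fits repeated dosing (5.3, 8.3, 10.1) means a reader cannot be certain that 4.2 governs.

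Three narrower objections are fair.

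- Individual packing is weak evidence for a single dose.
- The magnitude is assumed throughout; the documents support only one capsule against an unspecified number.
- The per-protocol consequence is limited. No section makes that set primary for efficacy, and the safety population needs only one use under either regimen.

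None of these resolves the contradiction.

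**Conclusion.** The concern holds. The protocol contains two incompatible dosing instructions, gives no course length for the daily one, and does not say which section prevails. This is more than missing detail: following 6.3 as written departs from 4.1 and 4.2, and this must be corrected before anyone is dosed.

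The documented discrepancy is 1 capsule against an unstated number. On the assumption of daily dosing from day 0 for between 3 and 28 days, the illustrative range is 3 to 28 capsules (29 if day 28 is included). The conclusion does not rest on any of those assumed durations, nor on mixed dosing having occurred. It rests on the wording of the four sections alone.

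**What to change.** **If a single dose is intended (the better reading).** Change section 3 of the Summary and section 6.3 to one capsule, once, on day 0. Move the empty-stomach instruction into 4.2, which lacks it. Delete the control-group line from 6.3 if the design stays one-arm.

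**If daily dosing is intended.** Correct 4.1 and 4.2 instead, state the number of days, and say whether days 7 to 28 are counted from the first or the last capsule.

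**In either case**

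- Define per-protocol completion in 10.1 and 10.2.1 by the chosen regimen.
- Make sure the existing distribution form and diary card show the number of capsules and the date of each. Their layouts are not in the documents, so they may already do so.
- If any subject has received more than the specified dose, report results by capsules received, using those records.

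**Cost.** A protocol clarification or amendment to the Summary and 6.3, with short additions to 4.2, 10.1 and 10.2.1. Section 12.4 requires a document signed by the main researcher and the sponsor before implementation, and a report to the ethics committee. No subjects, visits or new forms are added.

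A separate and lesser correction can go into the same amendment: the storage limit is 4°C in 6.1 but 23°C in 6.4 and 11.1, and one limit should be stated. Until then, keeping the product under 4°C satisfies both.

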### 4.2. Dose, method and course of treatment

Group	Dosage	Usage	Survey
Test group	1 Bacillus subtilis spore capsule at a time	Oral administration, once	28 days

Vaccine time window: Oral administration of the vaccine would be given immediately after the subjects were selected.

Essential medicines: over-the-counter medicines such as vitamins and minerals were allowed.

---

Medicines prohibited: antibiotics, thrombolytic drugs, anticoagulants, insulin,  $\beta$ -blockers, adenosine preparations, leucocyte adhesion inhibitors, other antioxidants, free radical scavengers, etc.

## 5. Subject selection

### 5.1. Inclusion criteria

Outpatient service (medical records of outpatient service shall be established), male or female, from 18 years old to 60 years old;

No hypertension, diabetes, hyperlipidemia and other basic diseases;

If the patient was a woman of gestational age, the pregnancy test at the time of screening should be negative; Contraception (oral or injectable contraceptives) should be used throughout the trial;

Obtained the informed written consent of the subject or the subject's immediate family member or the subject's guardian;

There was no serious cardiopulmonary liver and kidney insufficiency.

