### **6.5. Combination of medicines and prohibited medicines**

Other anti-influenza medicines should not be used during the trial.

---

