## 7. Clinical efficacy indexes and safety evaluation criteria

### 7.1. Main efficacy indicators

Immunogenicity of vaccines

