##### **7.4.1. When the test started**

Signed informed consent.

Inclusion criteria and exclusion criteria.

Medical history was collected and the status of medication was inquired.

Routine physical examination.

Routine laboratory tests: Routine blood examination (including erythrocyte count, leukocyte count, hemoglobin, platelet count, proportion of monocytes, lymphocytes and neutrophils), urine routine (erythrocyte, leukocyte, urine protein), liver and kidney function (including ALT, AST, TBIL, BUN, CR), pregnancy test (women of child-bearing age), and other laboratory examination.

Combination medication was recorded.

Assigned random numbers.

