#### 10.2.3. Analytical method

The experimental group was compared with the control group by superiority comparison.

Measurement data:  $X^2$  test, t-test, paired t-test, rank sum test, paired rank sum test and non-parameter test were used respectively statistical analysis to make statistical comparison and other methods.

Descriptive statistical analysis of side effect was performed.

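### COVID-19 history and pre-dose antibody are not specified, and no COVID-specific rule covers exposure before D28, so antibody from other sources cannot be separated from a response to the spore product

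*Combined protocol and SAP*

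**What the plan says.** **Eligibility.** Section 5.1 asks for outpatients aged 18 to 60 and, on health, "No hypertension, diabetes, hyperlipidemia and other basic diseases". Section 5.2 lists pregnancy, tumour, tuberculosis, dependence, allergy, interfering treatments and investigator discretion. Neither mentions past SARS-CoV-2 infection, COVID-19 vaccination or existing antibody.

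**D0.** Section 7.4.1 lists medical and medication history, physical examination, blood count, urine, and liver and kidney function. The list ends with "pregnancy test (women of child-bearing age), and other laboratory examination". No antibody, PCR or antigen test is named. Section 4.1 sets efficacy examinations for days 7, 14, 21 and 28. Section 7.4 puts a first examination at D0 but attaches the full set of trial indicators to the four later visits.

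**During follow-up.** Section 6.5 says "Other anti-influenza medicines should not be used during the trial". The prohibited list in 4.2 names no vaccine.

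**Endpoint and design.** The main indicator in 7.1 is "Immunogenicity of vaccines", and 7.2.1 adds a comparison with the immunogenicity of natural infection. Section 4.1 says "This study adopted a one-arm experimental design"; section 10.2.3 says "The experimental group was compared with the control group by superiority comparison".

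**Background.** The Introduction says of other products: "Some vaccines had been approved for conditional marketing or emergency use". It also reports that the spore product works in people not yet vaccinated: "it successfully increased the neutralizing antibody against sRBD in unvaccinated mice and human individuals after oral administration".

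**The concern.** A recovered or already vaccinated healthy adult meets every written criterion. The trial window in the Summary is April to September 2021, when by the protocol's own account other vaccines were available. Such a person may carry antibody to the same target before taking the capsule, and anyone infected or vaccinated between D0 and D28 may acquire it.

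Three things are at stake:

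- Attribution. In a one-arm study without a D0 titre, antibody found at D28 has no reference value.
- The population. The Introduction's claim concerns unvaccinated people, but no eligibility rule makes the trial population unvaccinated. In people already primed, the trial would measure boosting instead of a first response.
- The comparison in 7.2.1. Spore-induced and infection-induced immunogenicity cannot be contrasted cleanly if the spore group may include people who have been infected.

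**Working it through.** The documents give no sample size, standard deviation, response rate, assay or responder definition, so there is no planned figure to reproduce. The two routes of contamination behave differently and are taken separately. Every numerical input below is an assumption, except the two-sided 0.05 level from 10.2.4.

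**Route 1: antibody already present at D0.** Suppose the result is read as the share of subjects positive after dosing, with no D0 value. Let q be the share carrying antibody from elsewhere, all counted positive, and r the true response among the rest:

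apparent share = q + (1 − q) × r

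| q | r = 0 | r = 30% | r = 60% |
|---|---|---|---|
| 5% | 5% | 33.5% | 62% |
| 10% | 10% | 37% | 64% |
| 20% | 20% | 44% | 68% |
| 40% | 40% | 58% | 76% |

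For example, 0.20 + 0.80 × 0.30 = 0.44. If a D0 titre is taken and change from D0 is analysed, stable earlier antibody cancels. What remains is the mixing of priming and boosting.

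**Route 2: infection or another vaccine after D0.** Here a D0 titre does not help. Assume one exists, that the spore product does nothing, and that

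log10 change = N(0, 0.3) + δ × Bernoulli(p)

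where p is the share of subjects exposed by D28 and δ is 1.0 to 1.5 log10. The test is the paired t-test, t = mean ÷ (s/√n), counted when significant in the positive direction (nominal 2.5%). The apparent geometric mean rise is 10^(p × δ); for example, 10^(0.10 × 1.0) = 1.26. Simulated with 100,000 trials per cell:

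| p | Apparent rise | False positive, n = 30 | False positive, n = 50 |
|---|---|---|---|
| 1% | 1.02–1.04-fold | 3% | 4% |
| 2% | 1.05–1.07-fold | 4% | 5–6% |
| 5% | 1.12–1.19-fold | 8–9% | 13–17% |
| 10% | 1.26–1.41-fold | 20–25% | 35–47% |
| 20% | 1.58–2.00-fold | 56–68% | 82–92% |

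The ranges within cells run from δ = 1.0 to δ = 1.5. The result depends almost wholly on p, on which the documents are silent.

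**The case against.** Several provisions soften the point.

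- **Baseline sampling is unspecified, not ruled out.** The open-ended laboratory item in 7.4.1, the paired tests in 10.2.3 and the baseline indicators in 10.2.6 are all compatible with a D0 titre, and history taking could reveal past COVID-19. This stands as a limit on wording, but none of it requires an antibody result or a COVID-19 history.
- **Generic rules could catch some events.** Summary section 3 and section 6.3 allow no other medication, which may be read to bar a second vaccine. Section 5.4 lets the physician stop a subject whose new symptoms affect observation. Section 10.2.2 carries the previous value forward for lost cases. The per-protocol set leaves out users of banned medicines and major deviations. These rules are discretionary or indirect, and they miss silent infection.
- **A control group may exist.** Summary section 2 and sections 3, 6.3, 10.2.3 and 10.2.6 describe one, and 7.4.1 assigns random numbers. A randomised control would balance outside antibody on average. Summary section 4 and section 4.1 say one arm, so this relief depends on how the conflict is resolved. Even with a control, later exposures need an analysis rule.

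A reader might infer that the plan counts outside antibody as vaccine response. It has no responder definition, so the documents support only that the sources cannot be told apart. A reader might also take the Route 2 rates as the cost of failing to exclude prior infection. They are not: that model assumes a D0 titre, in which stable prior antibody cancels.

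**Conclusion.** The point holds as a gap in eligibility, baseline measurement and analysis rules. If the study is run as the one-arm trial that section 4.1 describes, the main result could not be attributed to the spore product, and the natural-infection comparison would be compromised.

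The size is unknown. Under Route 2 the false positive rate runs from close to nominal (3–4% at p = 1%) to 92% at p = 20%, assuming n = 30 to 50, SD 0.3 log10 and a rise of 1.0 to 1.5 log10. Nothing in the documents shows that 10% or 20% of subjects would be exposed within 28 days, so the upper rows are scenarios, not forecasts.

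It should still be settled before dosing, because a missing pre-dose titre cannot be recovered later unless serum was stored.

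**What to change.** 1. **Section 7.4.1:** record history of COVID-19 infection and vaccination. From the D0 blood draw, take pre-dose serum for anti-sRBD or neutralising antibody and for anti-N antibody.
2. **Sections 5.2 and 10.1:** exclude known prior infection or COVID-19 vaccination. Use the D0 serology to define a baseline-seronegative primary immunogenicity set, analysed as change from D0, and report seropositive subjects separately. Because serology defines an analysis set and not entry, dosing need not wait for the result, so this fits the immediate administration in 4.2.
3. **Sections 7.4 and 10.2:** record any COVID-19 vaccination or infection from D0 to D28, and test D28 serum for anti-N to find silent infection. Prespecify how titres after such an event enter the primary analysis, with an all-data sensitivity analysis.
4. **Design:** reconcile the one-arm statements with the control-group text.

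Other choices are defensible, such as stratifying or adjusting for baseline serostatus in place of restricting the primary set, or a different strategy for post-event titres. What matters is that one is fixed in advance.

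The cost is a short amendment, extra assays on blood already drawn, some screening losses and a smaller primary set.

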### 5.2. Exclusion criteria

Patients under 18 years of age or over 60 years of age;

Dementia who could not cooperate, or affecting the judgment of curative effect;

Women who were pregnant, breastfeeding or who might become pregnant during the study and who were not using effective contraceptives;

Patients suffering from tuberculosis, tumor and other organic lesions;

Known alcohol and drug dependence;

To determine the patients who were not suitable for this clinical observation;

People with coma, bleeding tendency and allergic constitution were excluded;

Treatments such as hormones, diuretics, hypertonic dehydrating agents, thrombolysis, anti-coagulation, and fibrillation that might affect the results of the study;

Staff directly involved in the study;

Other circumstances that other physicians or researchers had judged inappropriate for participating in the clinical trial

---

---

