### 12.3. Study subjects and informed consent

Prior to the inclusion of patients in the study, the investigator might provide a complete and comprehensive description of the purpose, procedures, and possible risks of the study to the patient or his or her designated representative. Patients should be made aware of their right to withdraw from the study at any time. Each patient might be given a written patient informed consent form prior to study. The study physician was responsible for obtaining signed informed consent form from each patient before the study and sending one of the signed informed consent forms to the subjects; The other was kept in the study archives. Any changes to the subject's informed consent might be documented and submitted to the IRB for approval. A copy of the new Informed Consent Form would be kept in the "Subject Informed Consent Form" file. Suggestions for modification were attached. The above changes could only be implemented if they were re-approved by the ERC, complied with the health regulations,

---

and signed by the participating institutions. Each subject or independent witness affected by the modification and any person involved in the informed consent discussion might sign and date two updated informed consent forms. He or she would be given a new form of informed consent. If the subject had a health care provider and agrees to notify the health care provider, it was recommended that the investigator explained the subject and the study to the subject's health care provider.

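### Section 5.1 accepts a relative's or guardian's consent in place of the subject's own, with no incapacity condition, in healthy adults aged 18 to 60, and so conflicts with section 12.3

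*Combined protocol and SAP*

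**What the plan says.** The inclusion criteria in section 5.1 contain one line on consent: "Obtained the informed written consent of the subject or the subject's immediate family member or the subject's guardian". It sets no order of preference among the three, does not require that the subject be unable to consent, and does not ask for the subject's assent.

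The population is described in several places. The Summary (item 5) has "Normal healthy people without disease". Section 4.1 has "qualified normal healthy people without disease from the hospital". Section 5.1 takes outpatients, "male or female, from 18 years old to 60 years old", with "No hypertension, diabetes, hyperlipidemia and other basic diseases".

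Section 12.3 sets out the consent procedure. On the signature it says "The study physician was responsible for obtaining signed informed consent form from each patient before the study". On the explanation of purpose, procedures and risks, it names the patient or a designated representative as the recipient.

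The dementia exclusion in section 5.2 is qualified: "Dementia who could not cooperate, or affecting the judgment of curative effect".

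**The concern.** Proxy consent exists for people who cannot decide for themselves. The population described here consists of healthy adults, with no minors and no emergency patients, and the protocol nowhere explains why a relative or guardian might need to sign for one of them. A site that checks only the eligibility list in 5.1 could count a relative's signature as sufficient for a capable adult.

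Two features raise the stakes. The product is an engineered spore displaying a viral antigen (section 1), given to people who are not ill. And section 4.2 has the dose follow selection immediately, so a consent error at entry would not be caught before the subject swallows the capsule.

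**Working it through.** No arithmetic applies. The check is to set the consent, population and dosing text side by side.

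| Section | What it says about who consents or signs | Direction |
|---|---|---|
| 5.1, consent criterion | Subject, immediate family member or guardian, as alternatives | Allows a proxy |
| 12.3, signature | Signed form from each patient, before the study | Requires the subject |
| 12.3, explanation | Given to the patient or a designated representative | Allows a proxy as recipient |
| 12.3, updated forms | After a modification, the subject or an independent witness, and those in the discussion, sign | Mixed |
| 5.4, definition of loss | Speaks of subjects having completed the form | Assumes the subject |
| 8.1, side-effect definition | Period begins when patients signed | Assumes the subject |
| 7.4.1, start of test | Consent is signed; no signatory named | Silent |

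Step 1. Does any section supply the condition that 5.1 lacks? None does. No section requires a capacity assessment, limits proxy consent to incapable subjects, or asks for assent.

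Step 2. Does 12.3 override 5.1? Its sentence on the signed form contradicts 5.1 if a proxy signs alone. But no section says which governs, and 12.3 weakens its own rule by allowing the explanation to go to a representative. Its next sentence says that patients should be told of their right to withdraw. If the explanation has gone to someone else, the section gives no separate route by which that information reaches the subject.

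Step 3. Does the stated population need a proxy route? Adults aged 18 to 60, attending as outpatients and described as healthy and without disease, do not. Comatose people are excluded in 5.2. Removing the proxy alternatives therefore excludes nobody the protocol intends to enrol.

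Step 4. How does the dementia line fit? It excludes dementia when the person cannot cooperate or when the assessment of effect would suffer. Neither condition concerns capacity to consent. In a population defined as free of disease, a partial exclusion of dementia is out of place: either the general definition already covers it, or the qualification implies that some dementia is acceptable. The two need to be squared.

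**The case against.** The strongest reply is that 12.3 is the operative consent procedure and 5.1 is only an entry in a checklist. Section 12.3 asks for a signed form from each patient, 5.4 and 8.1 take it for granted that the subject signs, and the designated representative appears only as a recipient of the explanation, not as a signatory. This stands in part. A reader might infer from 5.1 that the protocol plainly permits a capable adult to be enrolled without their own consent, or that every subject could enter that way. The documents do not support that reading, because it requires taking 5.1 alone and ignoring 12.3, 5.4 and 8.1. What remains is a contradiction that the protocol does not resolve.

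A reader might also infer that someone with mild dementia could enter on a guardian's signature. That route is largely closed. The healthy-population wording in the Summary and 4.1, the open-ended reference to other basic diseases in 5.1, and the investigator-discretion exclusions in 5.2 would ordinarily keep such a person out. The narrow dementia line is a drafting mismatch, not evidence of an open path.

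Finally, the consent form was not available for review, and the text reads like a literal translation, so resting everything on one conjunction calls for caution. Both are fair. The form may show that only the subject signs, but 5.1 would still need to be brought into line with it.

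**Conclusion.** The point holds as an internal contradiction about a basic safeguard, and it should be corrected. Section 5.1 states a consent rule that does not suit the population the protocol describes and that disagrees with 12.3, 5.4 and 8.1; nothing elsewhere removes the disagreement.

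It has no numerical size. No sample size, power or error rate depends on it, and the share of subjects who would enter by proxy cannot be derived. A reader might infer that data from subjects entered by proxy would have to be removed. The analysis-set definitions in 10.1 and 10.2.1 contain no such rule, so no loss of observations is claimed.

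The conclusion rests on two assumptions: that the criterion in 5.1 means what it literally says, and that the population is as described in the Summary, 4.1 and 5.1.

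**What to change.** Make three changes in one protocol amendment.

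1. In 5.1, require written informed consent signed by the subject personally, and delete the family-member and guardian alternatives.
2. In 12.3, delete the designated-representative alternative, so that the explanation of risks and of the right to withdraw goes to the subject.
3. Reconcile the qualified dementia exclusion in 5.2 with the definition of a healthy population in the Summary, 4.1 and 5.1.

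Check the consent form against the amended text at the same time. No rule on witnesses is proposed: 12.3 mentions an independent witness only for updated forms after a modification.

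The cost is a few wording edits and the ethics submission that goes with them. The only possible loss is a subject who could have entered only by proxy, and the stated population contains none.
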